To describe the occurrence of safety events including documented diagnosis of VOD/SOS, grade 3/4 TRAEs (lung/cardiac/kidney) and other liver dysfunction following InO initiation; in all patients and in patients with or without follow-up HSCT. In addition, to evaluate associations between risk factors identified in the INO-VATE ALL trial and risk for VOD/SOS in patients with follow-up HSCT.

The number of patients experiencing a documented diagnosis of VOD/SOS post-index, patients with an InO dose delay/reduction/discontinuation due to VOS/SOS, the number of patients experiencing a grade 3 or 4 TRAE (lung/cardiac/kidney) by type, treatments received for grade 3 or 4 TRAEs, dose delay/reduction/discontinuations for grade 3/4 TRAEs, the number of patients experiencing other liver dysfunctions and the associated treatments received and delay/reduction/discontinuations resulting will be presented as categorical variables (see Section 10.1.2). If sample size allows, this variable will be presented overall, and separately by grade, whether patient had follow-up chemotherapy after completion of chemotherapy or not and with follow up HSCT after HSCT or not. Treatments

for VOD/SOS will be presented as a categorical variable as per [Section 10.1.2](#). Survival after treatment will be presented as a binary variable (see [Section 10.1.4](#)). Peripheral blood counts prior to follow-up HSCT will be presented as quantitative data (see [Section 10.1.1](#)). The number and proportion of patients with significant risk factors for VOD/SOS measured at the time of follow-up HSCT, separately in patients developing and not developing VOD/SOS will be presented as categorical variables. The methodology for the evaluation of associations between risk factors will depend on whether there is any censorship of the data, if there is censoring a cox regression model will be used, otherwise, logistic regression and odds ratios will be used instead. The proportion of patients experiencing severe cytopenia will be presented as a binary variable.

10.2.9. Secondary Objective 8

Secondary objective 8: To describe overall HSCT rate and rate in patients going directly into HSCT (eg, without another induction therapy).

Overall HSCT rate will be calculated as the number of patients who have an HSCT after discontinuing InO divided by the total number of patients who discontinue InO for reasons other than death or being lost to follow-up while on InO. The rate in patients going directly into HSCT after InO discontinuation without another induction therapy will be calculated as the number of patients who go directly into HSCT without another induction therapy divided by the number of patient who have a follow-up HSCT post-InO discontinuation. Both of the above endpoints will be presented as binary variables as per [Section 10.1.4](#).

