9.2. Setting

[figure not shown]
Key definitions

- Index date: the date of initiation of the first cycle of InO.
- Baseline period: period from 6 months prior to index date to index date. The closest observation recorded during the baseline period and closest to index date will be used as baseline data (when more than one observations are available).
- Pre-index observation period: period from the date of ALL diagnosis to the index date.
- Post-index observation period: period from the index date until the date of death, or date of latest visit at the time of data collection, whichever is soonest.
- CR/CRI rate: number of patients who achieve CR/CRI divided by the total number of patients completing treatment with InO (defined as patients with a recorded date of discontinuation of InO).

- MRD negativity rate: proportion of patients in whom MRD-negative status is observed, among patients in whom MRD negativity status has been assessed, at any time until the end of treatment with InO (defined as the date of recorded discontinuation of InO).
- OS: time from index date to death.
- RFS: time from index date to the earliest date of the following events: death, progressive disease (including objective progression, relapse from CR/CRi, treatment discontinuation due to global deterioration of health status), and start of new induction therapy or post-therapy HSCT without achieving CR/CRi.
- NRM: Time from the date of follow-up HSCT until death without disease progression

Patients will be observed from the start of the pre-index observation period until the end of the post-index observation period. For the purpose of identifying risk factors for VOD/SOS and replicating the findings by Kantarjian et al.⁷, follow-up will be defined as the post-index observation period, and patients will be censored at the date of the last recorded clinic visit prior to data collection.

Figure 1: Study design and observation periods

Three to five of the 31 NHS Trusts participating in the CUP that treated the largest number of patients with InO as part of the CUP (total number of patients including private purchase to be confirmed) will initially be selected for this study to achieve a target sample size of approximately 25 patients (the number of sites may be expanded at a later date). The list of selected sites will be maintained in a stand-alone document. Sites will be selected on the basis that:

- Their cancer service participated in the CUP.

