
Number and proportion of patients with InO dose delay/reduction/discontinuation due to VOD/SOSNumber and proportion of patients experiencing grade 3/4 TRAEs (lung / cardiac / kidney) following InO initiation, by typeTreatments received and InO dose delay/reduction/discontinuation for grade 3/4 TRAEs (lung/cardiac/kidney)Number and proportion of patients experiencing other liver dysfunction following InO initiation, by typeTreatments received and InO dose delay/reduction/discontinuation for other liver dysfunctionPeripheral blood blast counts of patients prior to follow-up HSCTNumber and proportion of patients with significant risk factors for VOD/SOS measured at the time of follow-up HSCT (see below, extracted from Table 5 in Kantarjian et al.²), separately in patients developing and not developing VOD/SOS.	
prior to follow-up HSCT (HSCT recorded during the post-index observation period):
 
Date and results for peripheral blood blast counts closest prior to follow-up HSCTConditioning regimens prior to HSCT including Busulfan, other alkylating agents: names and date start, date end, full intensity / reduced intensity conditioningDate of HSCTDate of completion of chemotherapy treatment
---	--

Kantarjian et al⁷ identified risk factors for the occurrence of a documented diagnosis of VOD/SOS in patients who proceeded to follow-up HSCT after initiation of InO. The list of significant patient characteristics and transplant characteristics at the time of follow-up HSCT (with p-value<0.05) was as follows:

- Identified using univariate logistic regression:
 - Conditioning regimen with two alkylating agents (two versus one) prior to follow-up HSCT
 - Busulfan-containing regimen (yes versus no) prior to follow-up HSCT
 - Last bilirubin concentration (\geq Upper limit of normal [ULN] vs $<$ ULN) measured prior to follow-up HSCT
 - Age (\geq 55 years vs $<$ 55 years)
- Identified using multivariate logistic regression:
 - Conditioning regimen with two alkylating agents (two vs one) prior to follow-up HSCT
 - Last bilirubin concentration (\geq ULN vs $<$ ULN) measured prior to follow-up HSCT. Last AST or ALT concentration ($>1.5 \times$ ULN vs $\leq 1.5 \times$ ULN) measured prior to follow-up HSCT

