
 • Cycle number • PCR results providing percentage of leukaemic cells in bone marrow nucleated cells • Or alternatively, immunophenotyping by flow-cytometry results providing percentage of leukaemic cells in bone marrow nucleated cells 					
ALL diagnosis: • Date of first diagnosis.	✓	✓			

INOTUZUMAB
X9001222 NON-INTERVENTIONAL STUDY PROTOCOL
V1.0, 18 July 2019

Variables	Study time points				
	Pre-index observation period	Baseline	Index date	Post-initiation observation period	Other

 Phase of disease at receipt of Inotuzumab CR, 1st relapse, 2nd relapse, 3rd relapse, 4th or greater relapse CD22-expression test results: positive/negative Cytogenetic test result: MLL- AF4; BCR-ABL; low hypodiploid/near triploidy; complex karyotype e Relapsed at index date: Yes/No Refractory at index date: Yes/No 					
Liver diseases diagnosed prior to index date: 
 Name date diagnosis Diagnosed before/after ALL diagnosis at index date, ongoing / resolved 	✓	✓			
Full blood counts, date, result (including unit) for: 
 platelets ANC 		✓	✓		
Liver function tests: date, result and ULN for: 
 ALT AST ALP Bilirubin Albumin gamma glutamyl transferase. 		✓	✓	✓ for ALT, AST and bilirubin in patients with follow-up HSCT, at time of follow-up HSCT (up to 3 months before)	
Peripheral blood blast counts of patients				✓ in patients with	

PFIZER CONFIDENTIAL

INOTUZUMAB
X9001222 NON-INTERVENTIONAL STUDY PROTOCOL
V1.0, 18 July 2019

Variables	Study time points				
	Pre-index observation period	Baseline	Index date	Post-initiation observation period	Other
				follow-up HSCT, at time of follow-up HSCT (up to 3 months before)	
ALL relapses prior to InO: 
 • date of relapses • Name, start and stop dates, and best response to treatment for relapses prior to InO (list to be determined and may include: fludarabine- and anthracycline-containing regimens, blinatumomab) 					
Treatment history for ALL (all since diagnosis) prior to InO: 
 • 1st line chemotherapy according to national trial or treatment guideline • Blinatumomab treatment • Number of lines of salvage therapy • Prior HSCTs: number (0, 1, 2, ≥ 3) and type of conditioning regimen for each HSCT: high-dose myeloablative, reduced-intensity, nonmyeloablative • CAR T-cell therapies: number (0, 1, ≥ 2) 	✓	✓			

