3.1.1. Key Definitions

- *Index date: the date of initiation of the first cycle of InO.*

[figure not shown]
- *Baseline period: period from 6 months prior to index date. The closest observation recorded during the baseline period to the index date will be used as baseline data (when more than one observation is available).*
- *Pre-index observation period: period from the date of ALL diagnosis to the index date.*
- *Post-index observation period: period from the index date until the date of death, or date of latest visit at the time of data collection, whichever is soonest.*
- *CR/CRi rate: number of patients who achieve CR/CRi divided by the total number of patients completing treatment with InO (defined as patients with a recorded date of discontinuation of InO).*
- *MRD negativity rate: proportion of patients in whom MRD-negative status is observed, among patients in whom MRD negativity status has been assessed, at any time until the end of treatment with InO (defined as the date of recorded discontinuation of InO).*
- *OS: time from index date to death.*
- *RFS (interchangeable with EFS for the purpose of this SAP): time from index date to the earliest date of the following events: death, progressive disease (including objective progression, relapse from CR/CRi, treatment discontinuation due to global deterioration of health status) and start of new induction therapy or posttherapy HSCT without achieving CR/CRi.*
- *NRM: Time from the date of follow-up HSCT until death without disease progression or relapse. Deaths from any cause without prior progression are events. Events related to the disease such as relapse, progression are competing events, loss of follow-up are censored.*

Patients will be observed from the start of the pre-index observation period until the end of the post-index observation period. For the purpose of identifying risk factors for VOD/SOS and replicating the findings by Kantarjian et al¹ follow-up will be defined as the post-index observation period, and patients will be censored at the date of the last recorded clinic visit prior to data collection.

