Distribution of methods used to assess MRD negativity	All patients	Secondary Objective 3	None	Frequency tables and percentages.	Excluded.
Number and proportion of patients surviving at 3,6 and 12 months after InO initiation	All patients	Secondary Objective 4	Overall, and separately in patients with and without follow-up HSCT	Frequency tables and percentages.	Excluded.
Cause of death	All patients	Secondary Objective 4	Overall, and separately in patients with and without follow-up HSCT	Frequency tables and percentages.	Excluded.
Median OS (95% confidence interval)	All patients	Secondary Objective 4	Overall, and separately in patients with and without follow-up HSCT	Kaplan-Meier analysis, median OS measured as being from the date of InO initiation to the date of death. Patients alive at end of follow-up will be censored at date of last visit.	Standard imputation for dates (see Section 7). Otherwise excluded.
Proportion of patients who are relapse free at 3, 6 and 12 months after InO initiation	All patients	Secondary Objective 5	All patients, separately in patients with follow-up HSCT	Frequency tables and percentages.	Excluded.
Median RFS (95% CI)	All patients	Secondary Objective 5	All patients, separately in patients with	Kaplan-Meier analysis, from InO initiation to date of first relapse or date of	Standard imputation for dates (see Section 7).

PFIZER CONFIDENTIAL

Outcome	Analysis Set	Supports Protocol Objective Number	Subgroups	Statistical Method	Missing Data
			follow-up HSCT	last visit before data collection.	Otherwise excluded.
Median NRM (95% CI)	Patients undergoing follow-up HSCT	Secondary Objective 5	None	Kaplan-Meier analysis, from date of follow-up HSCT to date of death or the date of last visit before date of data collection. 95% CI will also be presented.	Standard imputation for dates (see Section 7). Otherwise excluded.
Proportion of patients initiated on each treatment	All patients	Secondary objective 6	Per treatment (chemotherapy (blinatumomab, other). HSCT, CAR T-cell therapy)	Frequency tables and percentages.	Excluded.
Response to treatment	All patients	Secondary objective 6	Per treatment (chemotherapy (blinatumomab, other). HSCT, CAR T-cell therapy)	Frequency tables and percentages.	Excluded.
Survival following treatment	All patients	Secondary objective 6	Per treatment (chemotherapy (blinatumomab, other). HSCT, CAR T-cell therapy)	Frequency tables and percentages.	Excluded.

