Number and proportion of patients with significant risk factors for VOD/SOS	All patients	Secondary Objective 7	All patients, separately in patients with follow-up HSCT	Frequency tables and percentages. Cox regression modelling investigating risk factor association with time to VOD/SOS. Alternatively, logistic regression and odds ratios will be used depending on whether the data is censored.	Excluded.
Overall HSCT rate	Patients who discontinue InO for reasons other than death or lost to follow-up while on InO treatment	Secondary objective 8	None	Frequency tables and percentages.	Excluded.
Rate of patients going directly into HSCT	Patients with follow-up HSCT	Secondary objective 8	None	Frequency tables and percentages.	Excluded.

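### VOD/SOS risk-factor analysis: the clock starts at first InO although the factors are measured at HSCT, and the Cox-or-logistic rule offers no real choice

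*SAP*

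**What the plan says.** Secondary objective 7 asks for associations between "risk factors identified in the INO-VATE ALL trial and risk for VOD/SOS in patients with follow-up HSCT". SAP 10.2.8 gives the method: "if there is censoring a cox regression model will be used, otherwise, logistic regression and odds ratios will be used instead". The matching row of SAP 10.2.11 reads "Cox regression modelling investigating risk factor association with time to VOD/SOS", again with logistic regression as the alternative. That row states no start date, and its analysis set is labelled as all patients.

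Follow-up for this analysis is set in SAP 3.1.1: "follow-up will be defined as the post-index observation period, and patients will be censored at the date of the last recorded clinic visit". Protocol 9.2 agrees: "follow-up will be defined as the post-index observation period". The post-index period begins at the first InO cycle. For NRM, by contrast, SAP 10.2.11 names a transplant origin: "Kaplan-Meier analysis, from date of follow-up HSCT to date of death or the date of last visit before date of data collection".

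The factors belong to the transplant.

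- SAP 4 names three: AST or ALT at or above ULN, bilirubin at or above ULN (both pre-HSCT), and dual alkylators in conditioning.
- Protocol 9.3 gives four factors from the trial's univariate analysis (two alkylators, busulfan, bilirubin, age), headed "Identified using univariate logistic regression". Its multivariate list has two alkylators and bilirubin, with AST/ALT above 1.5 x ULN running on inside the bilirubin bullet.
- For the laboratory values, protocol 9.3 asks for the last result before HSCT. Annex 2 ticks the post-index column "for ALT, AST and bilirubin in patients with follow-up HSCT, at time of follow-up HSCT (up to 3 months before").

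Protocol 9.5 adopts 10 events per variable and derives 45 HSCT patients (96 overall) for one factor and 90 (192 overall) for two. It allows a fallback from multivariate to univariate models where possible, and 9.9 warns that neither may be feasible. SAP 7.3 makes subgroup analyses depend on more than 5 patients, which is not an event count.

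**The concern.** The analysis is limited to patients who reach HSCT, and every listed factor except age is known only by reference to HSCT, yet time would run from first InO. Three things follow.

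- Time between InO and HSCT counts as time at risk, although each patient is in the analysis only because he or she survived to HSCT.
- At an event time measured from InO, the Cox risk set can contain patients not yet transplanted, already classified by conditioning and laboratory values they do not yet have.
- A VOD/SOS that began before HSCT would be an event attributed to factors measured afterwards. It could itself have raised the bilirubin or transaminase value then recorded as a pre-HSCT risk factor.

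The model rule looks wrong for a separate reason. Whether any observation is censored says little about whether a Cox model can be supported; the number of events decides that, and the rule does not mention it.

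At stake is one secondary result, but one that SAP 3.1.1 presents as replicating a published trial finding.

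**Working it through.** **1. Time origin.** Set side by side: the objective selects on HSCT; the factors are measured at HSCT; follow-up starts at first InO (SAP 3.1.1, protocol 9.2); the model row gives no other origin. No visible passage sets time zero at HSCT, delayed entry at HSCT, or time-dependent factors. The NRM row shows that an HSCT origin was written where it was intended.

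**2. The model rule.** Under SAP 3.1.1 an HSCT patient without VOD/SOS is censored at the last visit. Logistic regression is therefore reached only if every HSCT patient has VOD/SOS. With about 12 HSCT patients and the protocol's 22% rate, that chance is 0.22^12 = 1.3 x 10^-8 (at an assumed 50% rate, 0.5^12 = 2.4 x 10^-4). In that case the outcome would not vary and the logistic model could not be fitted. On a narrower reading, where event-free deaths are not called censored, a single surviving event-free patient still triggers Cox.

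**3. The protocol's sizes reproduce.** Inputs from protocol 9.5: 10 events per factor, 47% with HSCT (77/164), 22% VOD/SOS after HSCT.

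- One factor: 10/0.22 = 45.5, taken as 45; 45/0.47 = 95.7, so 96.
- Two factors: 2 x 45 = 90; 90/0.47 = 191.5, so 192.
- Three factors: 30/0.22 = 136.4; 136.4/0.47 = 290.1. With the protocol's rounding, 3 x 45 = 135; 135/0.47 = 287.2, so 288.

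**4. Events expected.** At N = 25: 25 x 0.47 = 11.75 HSCT patients and 11.75 x 0.22 = 2.6 events. Treating events as binomial with probability 0.47 x 0.22 = 0.1034 per enrolled patient:

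- P(0) = 0.8966^25 = 0.065
- P(0 or 1) = 0.0653 + 25 x 0.1034 x 0.8966^24 = 0.0653 + 0.1883 = 0.254
- P(at least 10) = 0.0001

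If all of the roughly 75 CUP patients were included, the mean is 75 x 0.1034 = 7.8 and P(at least 10) = 0.25.

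**5. Consequence for an ordinary estimate.** Factor prevalences are not in the documents, so this is an assumption: a binary factor unrelated to VOD/SOS, present in a of 12 HSCT patients. The chance that at least one level has no event is 0.78^a + 0.78^(12-a) - 0.78^12.

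| a | chance |
|---|---|
| 2 | 0.64 |
| 4 | 0.46 |
| 5 | 0.41 |
| 6 | 0.40 |

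No finite hazard ratio then exists, and no finite ordinary odds ratio either. With events in both levels, say 2/6 against 1/6, the exact 95% interval for the odds ratio is 0.09 to 176.

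**The case against.** The strongest reply is that the study is descriptive, has no hypothesis, and already concedes in protocol 9.5 and 9.9 that these models may not be possible. That stands, and it limits the weight of the point. But the concessions set no event threshold, and the 9.5 fallback is still a one-factor model, which by its own figures needs 96 patients. Sites may be added and NHS-commissioned patients come on top of the CUP, so the number may exceed 25; the rule would still need a condition.

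Cox is also a defensible method. Protocol 9.5 and 9.9 name it, and retrospective follow-up is unequal. A reader might infer that Cox is wrong because the trial used logistic regression. The documents do not support that: replicating a finding does not require the same effect measure, and an ordinary odds ratio fails under separation just as a hazard ratio does.

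On the laboratory values, a reader might infer that results 3 months old are planned. Protocol 9.3 asks for the last value immediately before HSCT; 3 months is an outer limit. Separate counts of VOD/SOS after HSCT are planned too (protocol 9.3, SAP 8), though the association model is not tied to them. The all-patients label is generic, and the objective itself restricts the association to HSCT patients.

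On the factors, a reader might infer that the protocol contradicts itself on two against three. That rests on a run-on bullet in 9.3, possibly a product of text extraction. The firmer difference is between 9.5 (two) and SAP 4 (three). Protocol 9.7 lets the SAP modify the plan, so the SAP's list and cut-off may be deliberate; the SAP does not say so.

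Finally, parts of protocol 9.7 are redacted and may hold model details. The point is confined to visible text.

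**Conclusion.** The plan should be changed before analysis on two counts.

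The time origin is wrong as written: follow-up starts at first InO for factors measured at HSCT, and no visible passage corrects it. A reader might infer that the association will be materially biased in a known direction. The documents do not support that, because they give no rate of VOD/SOS before HSCT. What can be said is that with 2 or 3 expected events, one pre-HSCT case would be a third to a half of them.

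The model rule is not a choice. It ends in Cox in practice, without an event condition, where 10 events have a probability of about 0.0001 at N = 25 and none or one about 25%. These figures assume that the trial's 47% and 22% carry over to this cohort.

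The differing factor list and AST/ALT cut-off are a matter for reconciliation. Patients with AST or ALT from ULN to 1.5 x ULN are classed differently by the two documents, and which cut-off matches the source cannot be judged here. The 90 and 192 in protocol 9.5 hold for two factors only.

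The effect is limited to one secondary association; the primary objective and the descriptive VOD/SOS counts are untouched.

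**What to change.** In SAP 3.1.1, 10.2.8 and 10.2.11:

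1. Set time zero for this analysis at the earliest follow-up HSCT, as SAP 10.2.6 does for NRM. Count only VOD/SOS with onset after it, and report earlier cases separately.
2. Restrict the association analysis in this row to patients with follow-up HSCT.
3. State how death without VOD/SOS is handled, for example as a competing event.
4. Delete the censoring-based rule. State that no unpenalised Cox or multivariate model is fitted below the protocol's own 10 events per factor. Below that, report the factor-by-VOD/SOS tables already planned, with exact intervals for the odds ratio (one-sided under separation), or a one-factor Firth-penalised model, either Cox from HSCT or logistic.
5. Reconcile the factor list and the AST/ALT analysis cut-off between protocol 9.3 and SAP 4, or state that the SAP departs from the protocol. If three factors are kept, restate 9.5 as about 136 HSCT patients and 290 overall (135 and 288 with its rounding).

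The cost is wording only: HSCT dates, VOD/SOS start dates and factor values are already collected (protocol 9.3 and Annex 2). The downsides are that no adjusted estimate is promised, any pre-HSCT VOD/SOS leaves the association analysis, and the tables ignore unequal follow-up, as would a logistic model. The intervals will be very wide, which reflects what so few events can show.
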